6.2.3. Subject Characteristics and Demographics

The subject's sex, weight, height, other demographic characteristics, and other baseline disease characteristics will be recorded. BMI and age will be calculated. Demographic and baseline characteristics will be summarized for each treatment group using the mITT population. For Part B, data will also be summarized using the PP population.

6.2.4. Previous and Concomitant Therapy

Previous therapy is defined as therapy for the primary disease that has been discontinued prior to screening, and concomitant therapy is defined as therapy that is ongoing during the study.

Previous therapy will be collected at screening. Concomitant therapy will be collected at each visit. The reported term will be classified by the WHO drug dictionary and summarized using number and frequency by WHO drug ATC classification and treatment group.

Previous and concomitant therapies for the primary disease collected at screening will be summarized by:

- Types and number of therapies (NSAIDs, corticosteroid, cDMARDs, biologic agents)
- Average daily dose of corticosteroid
- Average weekly dose of methotrexate
- Number and type of cDMARDs (methotrexate only, methotrexate + other cDMARD(s), non-methotrexate only)
- Number of previous biologic agents (0, 1, 2, ≥ 3), name of previous biologic agents, and type of biologic agents (anti-TNF, no anti-TNF).

Concomitant therapies, defined as therapies with a stop date on or after the date of the first dose of the study drug, used for the primary disease will be summarized as below:

- Types and number of therapies (NSAIDs, corticosteroid, cDMARDs)
- Average daily dose of corticosteroid
- Average weekly dose of methotrexate
- Number and type of cDMARDs (methotrexate only, methotrexate + other cDMARD(s), non-methotrexate only).

Concomitant therapies used for conditions other than the primary disease during the Dosing Period will also be summarized. New initiated concomitant therapies after the last study drug in the study follow-up period, defined as therapies with a start date on or after the stop date of the study drug, will be summarized.

The ATC code H02 will be used to select all possible corticosteroids (H02 Corticosteroids for systemic use with route of Oral). All unique preferred terms in the database falling under the ATC code in [Appendix 1](#) will be reviewed by the medical group in order to determine which ones should be included. All corticosteroid doses need to be converted to prednisone equivalent doses. If additional conversion factors are required, these will be added prior to database lock.

6.2.5. Pre-existing Conditions and Medical History

Pre-existing Conditions and Medical History will be coded by Medical Dictionary for Regulatory Activities (MedDRA, most current available version). Data will be listed and summarized by treatment, system organ class (SOC), and preferred term (PT).

Pre-existing condition is defined as a condition with a start date on or before the informed consent date. Pre-existing conditions will be used to derive treatment-emergent adverse events (TEAEs) (Section 6.4.2).

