[18] have evidence of or test positive for hepatitis B virus (HBV) at screening, defined as (1) testing positive for hepatitis B surface antigen OR (2) testing positive for anti-hepatitis B core antibody (HBcAb) AND positive for HBV DNA

Subjects whose results are HBcAb positive and HBV DNA negative may be enrolled in the study, according to investigator judgment. Subjects whose results are HBcAb positive and HBV DNA negative at screening will be monitored for HBV during the study as detailed in Section 8.4.7.1.

[19] have evidence of or test positive for human immunodeficiency virus at screening

[20] have symptomatic herpes zoster within 6 months prior to screening that constitutes a clinically significant risk to the subject (according to investigator judgment)

- [21] have active tuberculosis (TB) determined on the basis of a positive medical history, physical examination, or chest radiography (per local standard of care) or have exclusionary TB test results, which include either of the following:
- a positive tuberculin skin test (TST) result (defined as a skin induration >5 mm at 48 to 72 hours after the test date, regardless of Bacillus Calmette-Guérin vaccination history) or
 - a positive (or persistently indeterminate/invalid/borderline) interferon γ release test (eg, QuantiFERON[®]-TB Gold or T-Spot[®].TB)

The choice to perform either a TST or an interferon γ release test will be made by the investigator according to local licensing and standard of care. If the QuantiFERON-TB Gold is indeterminate or the T-Spot.TB is invalid or borderline, one retest is allowed according to investigator judgment. If the repeat test is also indeterminate, the subject will be excluded. The interferon γ release test can be used only in countries where it is licensed, and the use of this test is dependent on previous treatment(s).

Subjects with known latent TB should not undergo a TST or interferon γ release test and must have documentation of receiving at least 4 weeks of appropriate, ongoing latent TB therapy, according to local standard of care, prior to screening. Such patients must continue/complete appropriate latent TB therapy during the course of the study in order to remain eligible.

- [22] are at high risk of infection or have recent evidence of clinically significant infection, based on findings that include the following:
- fever of 100.5°F (38°C) or above at screening or baseline that is not due to the underlying autoimmune disease (eg, RA)

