8.2. Adverse Events

Investigators are responsible for monitoring the safety of subjects who have entered this study and for alerting Lilly or its designee to any event that seems unusual, even if this event may be considered an unanticipated benefit to the subject.

The investigator is responsible for the appropriate medical care of subjects during the study.

Investigators must document their review of each laboratory safety report.

The investigator remains responsible for following, through an appropriate health care option, AEs that are serious or otherwise medically important, considered related to the study drug or the study, or that caused the subject to discontinue the study drug before completing the study. The subject should be followed until the event resolves, stabilizes with appropriate diagnostic evaluation, or is reasonably explained. The frequency of follow-up evaluations of the AE is left to the discretion of the investigator.

Lack of drug effect is not an AE in this study because the purpose of the clinical study is to establish treatment effect.

After the ICF is signed, study site personnel will record via the eCRF the occurrence and nature of each subject's pre-existing conditions, including clinically significant signs and symptoms of the disease under treatment in the study. In addition, site personnel will record via the eCRF any change in the condition(s) and any new conditions as AEs. Investigators should record their assessment of the potential relatedness of each AE to protocol procedure or study drug, via the eCRF.

The investigator decides whether he or she interprets the observed AEs as reasonably possibly related to RA, study drug, study procedure, or other concomitant treatment or pathology. To assess the relationship of the AEs, the following is defined:

reasonably possibly related: reasonable and temporal possibility that there is a cause and effect relationship between the study drug and/or study procedure and the AE

The investigator answers yes/no when making this assessment.

Adverse events will be graded for severity as mild, moderate, or severe, except for rashes (AESIs), which will be graded according to the Common Terminology Criteria for Adverse Events.

Planned nonsurgical interventions should not be reported as AEs unless the underlying medical condition has worsened during the course of the study.

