6.1.2. Baseline Definition

The baseline will be defined as the last available value before the first administration of study drug for both efficacy analyses, including unscheduled measurements for both parts separately. In most cases, this will be the measure recorded on Study Day 1 (Visit 2 in Part A and Visit 102 in Part B). Change from baseline values will be calculated as the postbaseline value minus the baseline value for each scheduled postbaseline time point. If the baseline value is missing (ie, no screening values, no Day 1 value, and no unscheduled measurements), the change from baseline will be missing as well.

For safety analyses, the baseline includes all pre-existing conditions recorded and any adverse events (AE) recorded before the first dose of study drug. Detailed definitions for each period of the studies are described in Section 6.4.2.

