6.4.2. Adverse Events

Adverse events (AEs) will be classified by SOC and PT as defined by the MedDRA®.

A TEAE is defined as an event that first occurs or worsens in severity after baseline. The MedDRA Lowest Level Term (LLT) will be used in the treatment-emergent computation. The maximum severity for each LLT during the baseline period will be used as baseline. The Dosing Period will be included as postbaseline for the analysis. Events with a missing severity during the Dosing Period will be considered treatment-emergent. Events at baseline with missing severity and reports with severity change during the Dosing Period will be considered as treatment-emergent. For events occurring on the day of first taking study medication, the case report form (CRF)-collected flag will be used to determine whether the event was pre- versus post-treatment.

	Baseline	Postbaseline	Analysis
Part A			
Dosing Period	All pre-existing conditions recorded at Visit 1 and any AEs recorded before the first dose of study drug (during the interval between Visits 1 and 2 and recorded with the time of onset before the first dose of study drug)	Dosing period (during the interval between Visits 2 and 5)	All AE analyses
Follow-up	All AEs recorded during the last visit before discontinuing study drug.	Safety follow-up period (during the interval between Visits 5 and 801)	Only for post-exposure emergent AE by SOC and preferred term.
Part B			
Dosing Period	All pre-existing conditions recorded at Visit 101 and any AEs recorded before the first dose of study drug (during the interval between Visits 101 and 102 and recorded with the time of onset before the first dose of study drug)	Dosing period (during the interval between Visits 102 and 106)	All AE analyses
Follow-up	All AEs recorded during the last visit before discontinuing study drug.	Safety follow-up period (during the interval between Visits 106 and 802)	Only for post-exposure emergent AE by SOC and preferred term.
Long-term Extension			
Dosing Period	Any AEs recorded during the interval between Visits 105 and 106 and recorded with the time of onset before the first dose of study drug for the long-term extension.	Dosing period (during the interval between Visits 106 and 114)	All AE analyses
Follow-up	All AEs recorded during the last visit before discontinuing study drug.	Safety follow-up period (during the interval between Visits 114 and 805)	Only for post-exposure-emergent AE by SOC and preferred term.

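### SAP 6.2.5 defines a pre-existing condition by start date alone, so on a literal reading a resolved illness can stop a new on-drug episode of the same LLT from counting as a TEAE

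*SAP*

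**What the plan says.** SAP 6.2.5 gives the definition: "Pre-existing condition is defined as a condition with a start date on or before the informed consent date". The next sentence says these conditions are used to derive TEAEs. The section title also names medical history, but no rule says which conditions belong there instead.

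Three further statements in the SAP complete the rule:

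- 6.1.2: "For safety analyses, the baseline includes all pre-existing conditions recorded and any adverse events (AE) recorded before the first dose of study drug".
- 6.4.2, the test: "A TEAE is defined as an event that first occurs or worsens in severity after baseline".
- 6.4.2, the comparator: "The maximum severity for each LLT during the baseline period will be used as baseline". The Part B baseline cell of the table in that section reads "All pre-existing conditions recorded at Visit 101 and any AEs recorded before the first dose of study drug", and the Part A cell is the same for Visit 1.

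Protocol 9.5.1 uses the same first-occurrence-or-worsening test and the same baseline content. Protocol Appendix 1 is broader: an event is treatment-emergent if it arises or gets worse at any point after baseline, with no condition that it be the first. Protocol 8.2 has sites record pre-existing conditions and then "any change in the condition(s) and any new conditions as AEs".

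**The concern.** A start date on or before consent is also true of an illness that began and ended years earlier. If such an illness is in the dataset with a severity, it sets the baseline for its LLT. A fresh episode on study drug then counts only if it is more severe than the old one.

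Safety is a primary objective in both parts. Treatment emergence feeds the TEAE tables (SAP 6.4.2), the treatment-emergent infection groups and potential opportunistic infections (6.4.5.6), anaphylaxis (6.4.5.7), the GI-injury listing (6.4.5.8) and the registry table of other AEs (6.5.4). Subjects with relevant history can enrol. Exclusion criterion [20] covers those who "have symptomatic herpes zoster within 6 months prior to screening", and only where the investigator sees a clinically significant risk. Criterion [22] sets the same 6-month window for serious opportunistic or chronic/recurring infection. The drug inhibits B-cell-receptor signalling, so a repeat of an earlier infection is an event the safety tables should be able to show.

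**Working it through.** The plan states no figure on this point, so there is none to reproduce. The check applies the rule and then sizes the loss under stated assumptions.

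**Step 1: the rule applied.** As written, the baseline is every recorded condition of the same LLT that started on or before consent. An on-drug event is a TEAE if there is no such record or if its severity exceeds the baseline maximum. The alternative rule also requires the condition to be ongoing at consent.

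| History of the LLT | On-drug severity | As written | Ongoing required |
|---|---|---|---|
| none | mild, moderate or severe | TEAE | TEAE |
| moderate, resolved before consent | mild | not TEAE | TEAE |
| moderate, resolved before consent | moderate | not TEAE | TEAE |
| moderate, resolved before consent | severe | TEAE | TEAE |
| moderate, ongoing | mild or moderate | not TEAE | not TEAE |
| moderate, ongoing | severe | TEAE | TEAE |

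The rules differ only for resolved history followed by an on-drug episode of equal or lower severity.

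**Step 2: consistency with other text.**
- Under protocol Appendix 1 the two cells that change would be TEAEs.
- SAP 6.2.4 separates previous from concomitant therapy by whether the therapy had stopped. SAP 6.2.5 has no parallel condition.
- The long-term-extension baseline in SAP 6.4.2 uses only AEs recorded between Visits 105 and 106. The same recurrence in a subject with remote history could therefore be emergent in the extension but not in Part B.

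**Step 3: size.** The documents give no history rates, so all inputs here are assumptions. Let h be the share of subjects with a resolved, severity-graded earlier episode of the same LLT at equal or higher severity. Let k be their risk of a new episode relative to other subjects.

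Lost share = hk / (1 − h + hk)

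| h | k = 1 | k = 2 | k = 3 |
|---|---|---|---|
| 2% | 0.02/1.00 = 2.0% | 0.04/1.02 = 3.9% | 0.06/1.04 = 5.8% |
| 5% | 0.05/1.00 = 5.0% | 0.10/1.05 = 9.5% | 0.15/1.10 = 13.6% |

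**Step 4: effect on an arm comparison.** Take 61 subjects per arm (the planned Part B size), an assumed true incidence for one LLT of 20% versus 10%, k = 1 and the same h in both arms.
- No loss: 61 × 0.20 = 12.2 versus 61 × 0.10 = 6.1 subjects; difference 10 points.
- h = 5%: 61 × 0.19 = 11.6 versus 61 × 0.095 = 5.8; difference 9.5 points.
- h = 10%: 61 × 0.18 = 11.0 versus 61 × 0.09 = 5.5; difference 9 points.

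The ratio stays at 2. Counts and the absolute difference shrink by the factor 1 − h.

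**The case against.** The best defence is that the text need not be applied this way.

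- **Resolved illness may not be in the dataset.** SAP 6.2.5 and the Schedules of Activities name medical history as well as pre-existing conditions, and protocol 8.2 speaks of conditions that can change, which fits present illness. A reader might infer that every resolved history item becomes baseline. The documents do not show that, because the eCRF is not among them.
- **The comparator is tied to the baseline period.** An illness that ended years before consent had no severity in that period. This is a fair reading of one sentence in SAP 6.4.2, but the table in the same section admits all recorded pre-existing conditions, so the text does not settle the matter.
- **Severity may be missing.** No passage says resolved history is graded. The missing-severity sentence in SAP 6.4.2 might rescue such cases, but it also refers to a severity change, so the rescue is unclear.
- **Matching is narrow.** A recurrence coded to another LLT still counts. In a group such as all infections, a subject drops out only if every one of that subject's events in the group is suppressed.
- **Some groups are poor examples.** Exclusions [17], [18], [21] and [28] should make earlier episodes of the same LLT uncommon for viral hepatitis, tuberculosis and anaphylaxis.

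These points limit the size, and they stand. They do not supply the missing condition: no sentence in either document says that a condition which ended before consent is left out of the TEAE baseline.

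A reader might also infer a large loss of events and a marked loss of power in the safety comparisons. The documents support neither. Nothing in them ties h to 10% or more. Scaling a group-level rate by an LLT-level share mixes two levels. SAP 6.1 and 6.4 also call the safety tests descriptive rather than formal hypothesis tests.

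**Conclusion.** The point holds as a wrongly specified derivation rule with an effect of unknown and probably modest size. Taken literally, SAP 6.2.5, 6.1.2 and 6.4.2 together remove some new on-drug episodes from the TEAE counts, against protocol Appendix 1. Protocol 9.5.1 shares the SAP's wording, so the protocol is also divided within itself.

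The loss arises only if the earlier illness was recorded as a pre-existing condition, carried a severity, falls under the same LLT and was at least as severe as the new episode. For an assumed h of 2% to 5%, the LLT-level loss is 2% to 5% with no change in risk, and 4% to 14% if recurrence risk is two to three times as high. Group-level losses would usually be smaller. If h and k are equal across the randomised arms, the drug-to-placebo ratio is preserved, and the harm is lower counts and a smaller absolute difference. No power loss should be claimed.

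Not obviously affected are the SAE and AE-discontinuation summaries (SAP 6.4.2.1 and 6.4.2.2, not stated as limited to TEAEs), the rash AESI count (6.4.5.2, taken from its own eCRF form) and the listings of all AEs.

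**What to change.** - **SAP 6.2.5:** define a pre-existing condition as one that started on or before consent and is ongoing at consent, meaning that it has no end date or has an end date on or after consent. Class conditions that ended earlier as medical history, to be summarised but not used as TEAE baseline.
- **SAP 6.1.2 and the Part A and Part B baseline cells of the 6.4.2 table:** carry the same restriction.
- **Protocol 9.5.1:** state in the SAP that its baseline wording is read the same way, which brings it closer to Appendix 1.

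The cost is a few sentences and one programming condition. If the derivation is already programmed this way, the edit only makes the SAP say so. TEAE counts may rise slightly in all arms. One gap stays open: AEs that start after consent and resolve before the first dose remain baseline under SAP 6.4.2.

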6.2.6. Treatment Compliance

Treatment compliance will be evaluated by visit and dosing period, including the date study drug was dispensed, the number of tablets dispensed, and the number of tablets returned. One dose is defined as 4 tablets. These data and the number of days of exposure will be used to calculate the percent compliance (percent compliance = number of doses taken divided by the days of exposure multiplied by 100). A subject will be classified as compliant if the subject takes the assigned study drug 80% to 120% of the time, during the Dosing Period.

Number of doses taken, days of exposure, percent compliance, and number and percentage of subjects compliant will be presented by visit.

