6.7. Treatment Compliance

Subject compliance with study medication will be assessed at each visit. Compliance will be assessed by counting returned tablets of study drug. Deviation(s) from the prescribed dosage regimen should be recorded in the electronic case report form (eCRF).

A subject will be considered significantly noncompliant if he or she misses more than 20% of the prescribed doses during the study. Similarly, a subject will be considered significantly noncompliant if he or she is judged by the investigator to have intentionally or repeatedly taken more than the prescribed amount of medication. Subjects found to be noncompliant with the study drug should be assessed to determine the reason for noncompliance and educated and/or managed as deemed appropriate by the investigator to improve compliance, or they should be discontinued from the study.

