[15] and [16] clinically significant safety labs at screening	Programmable (Clinical database)	if any of lab result for selected lab tests is outside of exclusionary range (stated in protocol exclusion 15 & 16) at screening	No
[17], [18],[19] Evidence of hepatitis B, C or HIV	Programmable (Clinical database)	If HIV, HBV, or HCV is positive at screening.	Yes

Category / Subcategory / Study specific	Source	Methods of Identification	Excluded from the Per Protocol Analysis
Category: Investigational Product			
Treatment Assignment	Non Programming (Monitoring)	Dispensing error: Subject is assigned to A, but site gave B to the subject	Yes
Dosing Error	Non Programmable (Monitoring)	- All issues referred to Incorrect dosing	Yes
Non-Compliance	Programmable (clinical database)	Treatment compliance below 80% or over 120%	Yes
Shipment and Storage	Non Programmable (Monitoring)	Temperature control for drug storage or biological samples not kept	Yes
Drug Accountability	Non Programmable (Monitoring)	- IP was not returned by subject/IP lost by subject or at site - Empty or unused IP packaging was not returned or lost by the subject more than once	No
Unblinding	Non Programmable (Monitoring)	- Any inadvertent unblinding affecting, subjects, investigator or sponsor	Yes, for any visit after the unblinding?
Category: Study Procedures			
Excluded Con-Meds	Mixed (Clinical database and Monitoring)	Study specific Definition: a list with all concomitant medication will be generated, and CRP will flag those excluded (the flagged medications will be used in programming to flag important protocol deviations)	Yes
Category: Administrative/Oversight			
Subcategory:			
Improper Conduct of Assessments	Non Programmable (Monitoring)	Unauthorized/Unqualified site personnel perform study related activities. Study personnel training not performed, not properly documented Non Programmable (Monitoring)	Yes
Suspected Misconduct	Non Programmable (Monitoring)	- Site staff sharing IWRS, EDC or ePresentOnline account details - Suspected falsification of data	Yes if suspected falsification of data
Category: Safety			
Subcategory:			
Safety Mailings	Non Programmable (Monitoring)	Lack, significant delay in safety mailing review (significant delay defined as a delay of 6 months)	No

Category / Subcategory / Study_specific	Source	Methods of Identification	Excluded from the Per Protocol Analysis

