6.4.1. Exposure to the Drug

Duration of exposure will be calculated for each subject and summarized by treatment group.

For subjects without drug interruption, the duration of exposure for each subject is the date of last dose – date of first dose +1. If subjects have drug interruption, the duration of exposure for each subject is the (Treatment end date before drug interruption – date of first dose +1) + (date of last dose – treatment re-start date +1).

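### Compliance is divided by days of exposure, so tablets skipped after the last dose or in a recorded interruption are not counted as missed

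*SAP*

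**What the plan says.** Protocol 6.7 assesses compliance by counting returned tablets. It calls a subject significantly noncompliant who "misses more than 20% of the prescribed doses during the study", so its basis is what was prescribed.

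SAP 6.2.6 sets the calculation: "percent compliance = number of doses taken divided by the days of exposure multiplied by 100". It adds that "One dose is defined as 4 tablets", and it classes a subject as compliant who "takes the assigned study drug 80% to 120% of the time, during the Dosing Period". It does not define days of exposure and cites no other section.

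The SAP's only definition is in 6.4.1. Without an interruption, "the duration of exposure for each subject is the date of last dose – date of first dose +1". With one, the formula is "Treatment end date before drug interruption – date of first dose +1) + (date of last dose – treatment re-start date +1", so the days between stop and restart drop out.

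In SAP Table JPDA.6.1 the Non-Compliance deviation is "Treatment compliance below 80% or over 120" percent, and it excludes the subject from the per-protocol analysis. Separately, SAP 6.1.1 and the text after that table require 12 weeks of study drug for the per-protocol set.

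**The concern.** The two documents measure compliance against different denominators. Under the SAP's ratio, read with 6.4.1, a day after the last tablet or inside a recorded interruption adds nothing to doses taken and nothing to days of exposure, so it cannot count as missed. The ratio therefore describes tablet-taking while on drug, but it is labelled and used as compliance over the Dosing Period. SAP 6.2.6 is also at odds with itself, because it classifies subjects over the Dosing Period with a percentage computed over exposure.

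Two outputs are at stake: the compliance table, and the compliance criterion for the per-protocol set, which supports the sensitivity analysis of ACR20 and the repeats of the key secondary analyses.

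**Working it through.** The plan states no compliance figure to reproduce. The check applies both definitions to the same example subjects.

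Inputs:
- Doses taken, D, in units of four tablets (SAP 6.2.6).
- Days of exposure, E, from SAP 6.4.1.
- Prescribed doses in Part B: 84. This is an assumption, 12 × 7, from once-daily dosing from Week 0 through Week 12 (Protocol Appendix 2). The documents give no count.
- Week 12 visit: Day 85 ± 3, that is Day 82 to Day 88 (Protocol Appendix 2).
- Thresholds: more than 20% missed (Protocol 6.7); below 80% (SAP Table JPDA.6.1).

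Formulas:
- SAP basis: 100 × D / E
- Protocol basis: 100 × D / 84

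Since 16/84 = 19.0% and 17/84 = 20.2%, the protocol's threshold is first crossed at 17 missed doses.

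| Example subject | D | E | SAP basis | Protocol basis |
|---|---|---|---|---|
| Last tablet Day 63, no discontinuation recorded, attends Week 12 | 63 | 63 | 100% | 75.0% |
| 21-day gap, entered as an interruption | 63 | 84 − 21 = 63 | 100% | 75.0% |
| 21-day gap, not entered as an interruption | 63 | 84 | 75.0% | 75.0% |
| 17-day gap, entered as an interruption | 67 | 84 − 17 = 67 | 100% | 79.8% |
| 17 scattered missed doses | 67 | 84 | 79.8% | 79.8% |
| Last tablet Day 60, 12 scattered misses before it | 48 | 60 | 80.0% | 57.1% |

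The first result does not depend on the exact figure of 84. If the denominator runs from first dose to the Week 12 visit, the window gives 63/82 = 76.8% to 63/88 = 71.6%, below 80% throughout.

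Rows 2 and 3 show that the same tablet-taking scores 100% or 75% according to how the gap is entered. Row 5 shows that scattered misses are still caught. Row 6 shows that a partial shortfall can be lifted to the compliant boundary.

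**The case against.** Several points on the other side have force.

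- **Early stopping and the per-protocol set.** A reader might infer that the per-protocol set retains subjects who stop early. The documents do not support that: 12 weeks of study drug is a separate condition, so the Day 63 subject should be excluded whatever the percentage says. For early stoppers the error is largely confined to the compliance table.
- **Recorded discontinuation.** Protocol 7.1.2 says that subjects who stop study drug should also leave the study. Ending the count at a recorded permanent discontinuation is therefore defensible, and the fix below does the same. The problem is undeclared stopping before Week 12, and the documents do not say how the last-dose date is recorded in that case.
- **Self-directed gaps.** A reader might infer that any pause by the subject disappears. It does so only if entered as a drug interruption. Protocol 7.1.1 and 8.4.6 describe interruptions as the investigator's decision, and Protocol 6.7 has deviations from the regimen recorded in the eCRF without calling them interruptions. If they are not entered as interruptions, a 21-day gap scores 75% and is caught.
- **The link to 6.4.1.** It is inferred. SAP 6.2.6 reports by visit, while 6.4.1 gives one duration per subject, and the reference to the Dosing Period could suggest a full-period basis. But 6.2.6 states its divisor and the SAP offers no other meaning for it. At the least, the term needs a definition.
- **Undefined prescribed doses.** The protocol does not define them. Doses withheld on the investigator's instruction may not count as missed.

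**Conclusion.** The concern holds as a conflict between SAP 6.2.6, read with 6.4.1, and protocol 6.7. For a subject who silently stops at Day 63 it is worth about 25 percentage points (100% against 75%, or 71.6% to 76.8% over the visit window). For a 21-day self-directed gap it is worth 25 points if the gap is entered as an interruption and nothing if it is not.

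The practical effect is limited. The compliance table is inflated. In the per-protocol set the clear gap is the subject who restarts after a recorded interruption and reaches Week 12: compliance can read 100%, and the 12-week requirement sets no limit on gaps. How many subjects this affects cannot be estimated from the documents.

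A reader might also infer that the primary result is at risk. It is not: the primary analysis uses the mITT population with non-responder imputation and does not use compliance.

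The conclusion rests on three assumptions: days of exposure in 6.2.6 means the 6.4.1 duration; 84 doses are prescribed; and, where 100% is shown, every day counted as exposure was dosed.

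**What to change.** In SAP 6.2.6, define the denominator as scheduled dosing days in the visit interval or in the Dosing Period. For the latter, count from first dose to the Week 12 visit, or to recorded permanent discontinuation if that is earlier. Subtract only interruptions recorded as investigator-directed. If the reason for an interruption is not captured, subtract none, and report exposure-based adherence separately under its own name. Make Table JPDA.6.1 refer to this definition, and align both with protocol 6.7, including what counts as a prescribed dose.

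Whether a long investigator-directed gap should disqualify a subject from the per-protocol set is a separate choice that this formula does not settle.

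The cost is one changed formula and a line of definition. Dosing, visit and discontinuation dates are already collected, and Protocol 8.4.6 asks for stop and restart dates when drug is interrupted for rash. The sponsor must confirm whether the reason for each interruption is recorded, since the documents do not show that it is.
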